This study has two primary objectives. First, to evaluate changes in respiratory drive and inspiratory effort—measured by Pocc, PMI, and P0.1—and corresponding Vt across varying levels of pressure support in surgical ICU patients after major abdominal surgery who require prolonged mechanical ventilation (>48 hours)⁽¹⁷⁾. Second, we aim to determine the incidence of inadequate assistance (active, quasipassive)⁽⁷⁾ in patients receiving PSV and explore its association with relevant clinical outcomes.

Study Design

This is a prospective, single-center, observational physiological study conducted in the surgical intensive care unit (ICU). A repeated-measures design is employed to systematically evaluate the effects of pressure support (PS) level adjustments on respiratory effort, drive, and diaphragmatic function in mechanically ventilated patients.

Study Population

Inclusion Criteria

- Adult patients (age ≥ 18 years) admitted to the surgical ICU.
- Recent major abdominal surgery requiring postoperative ICU care
- Receiving invasive mechanical ventilation for more than 48 hours
- Clinically stable, with no plan for extubation within 6 hours of study enrollment.

- Able to tolerate short-term adjustments in pressure support (PS) level as per protocol.

Exclusion Criteria

- Known neuromuscular diseases affecting respiratory muscle function.
- Hemodynamic instability requiring escalation of vasopressor support.
- Severe hypoxic respiratory failure requiring PEEP >10 cmH₂O or FiO₂ >60%.
- Deep sedation (Richmond Agitation-Sedation Scale [RASS] score < -3) or ongoing neuromuscular blockade.
- History of chronic obstructive pulmonary disease (COPD) or other obstructive lung diseases.

Intervention / Protocol

After confirming eligibility and obtaining informed consent (from patients or legally authorized representative), enrolled patients will undergo a standardized stepwise adjustment of pressure support (PS) levels while remaining in pressure support ventilation mode. During the protocol, Automatic Tube Compensation (ATC) will be turned off to avoid interference with respiratory measurements. This protocol was adapted from Doccia et al. ⁽⁷⁾. Measurements will be performed once daily for up to three consecutive days or until the patient is extubated—whichever occurs first.

Pressure Support Steps

Patients will be studied at six PS levels in the following sequence:

[figure not shown]
- Baseline PS (clinically set level)
- Baseline -6 cmH₂O
- Baseline -3 cmH₂O

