- Return to baseline PS
- Baseline +3 cmH₂O
- Baseline +6 cmH₂O

The order of the four non-baseline steps will be randomized for each patient using sealed envelopes, while the baseline PS step will be performed first and repeated last to assess measurement reproducibility.

At each pressure support (PS) level, a 2-minute stabilization period will be followed by three consecutive measurements of the following parameters: tidal volume (V_t), respiratory rate, P_{0.1}, P_{occ}, pressure muscle index (PMI), static compliance of the

respiratory system (Crs), and peripheral oxygen saturation (SpO_2). Vt , RR , P0.1 , Pocc , PMI , and Crs will be obtained from the ventilator, while SpO_2 will be recorded from the ICU monitor. PMI will be calculated as $\text{PMI} = \text{Pplat} - (\text{PEEP} + \text{PS})$, and Crs as $\text{Crs} = \text{Crs} = \text{Vt} / (\text{Pplat} - \text{PEEP})$. All values will be averaged across the three readings. **Figure 1. Study**

Protocol Flowchart

Measurements and Outcomes

Primary Outcome

- To evaluate changes in respiratory drive and inspiratory effort—quantified using P0.1, maximum negative occlusion pressure (Pocc), and pressure muscle index (PMI)—across varying levels of pressure support in adult surgical ICU patients after major abdominal surgery.

Secondary Outcomes

- To quantify the incidence of quasi-passive and active response patterns during pressure support ventilation, based on physiological criteria derived from patient responses.
- To assess the relationship between these ventilatory response patterns and clinical outcomes, including duration of mechanical ventilation, ICU length of stay, reintubation or non-invasive ventilation use, and ICU/hospital discharge disposition.

Definition of ventilatory response patterns:

- An active pattern is characterized by relatively stable V_t and plateau pressure despite reductions in pressure support, accompanied by a compensatory increase in PMI—indicating greater patient-driven effort. In contrast, a quasi-passive pattern is marked by a progressive decline in V_t and plateau pressure with little or no change in PMI, suggesting limited patient contribution to ventilation. ⁽⁷⁾
- As no standardized thresholds currently exist, these classifications will be determined post hoc based on individual response trends observed in the study dataset.

Data Collection

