The calculated minimum required sample size is 20 patients. To improve the precision of subgroup analyses, enhance generalizability, and account for possible dropouts or incomplete data, we plan to enroll a total of 40 patients.

Statistical Analysis

Descriptive statistics will be used to summarize baseline characteristics. Continuous variables will be presented as mean \pm standard deviation or median (IQR), depending on distribution. Categorical variables will be summarized as counts and percentages.

Primary analysis:

- Repeated-measures ANOVA or Friedman test (non-parametric) will be used to assess changes in PMI, Pocc, and P0.1 across PS levels.
- Post-hoc pairwise comparisons will be performed with Bonferroni correction.

Secondary analysis:

- Pearson or Spearman correlation will be used to evaluate relationships between effort indices (PMI, Pocc, P0.1).
- Linear mixed models will explore associations between PS levels and effort parameters, accounting for intra-patient variability.
- The incidence of under- and over-assistance will be described, and logistic regression may be used to assess their associations with clinical outcomes (e.g., prolonged ventilation).

A p-value <0.05 will be considered statistically significant. Statistical analyses will be performed using R.

Ethical Considerations

- Study protocol to be approved by institutional ethics board.
- Written informed consent obtained from patient or surrogate.
- Minimal risk as PS level adjustments are brief and within clinically accepted ranges.

References

1. van Oosten JP, Akoumianaki E, Jonkman AH. Monitoring respiratory muscles effort during mechanical ventilation. *Curr Opin Crit Care*. Feb 1 2025;31(1):12-20. doi:10.1097/mcc.0000000000001229

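### The planned Pearson or Spearman correlations between PMI, Pocc and P0.1 state no unit of analysis; read plainly, they pool repeated steps and days as independent and blend within- and between-patient relations

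*Protocol*

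**What the plan says.** The first bullet under Secondary analysis in the protocol's Statistical Analysis section reads "Pearson or Spearman correlation will be used to evaluate relationships between effort indices (PMI, Pocc, P0.1"). It names no step, day, per-patient summary or method for clustered data.

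The rest of the protocol describes data that are clustered by construction:

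- Study Design: "A repeated-measures design is employed to systematically evaluate the effects of pressure support (PS) level adjustments on respiratory effort".
- Pressure Support Steps: "Patients will be studied at six PS levels in the following sequence". These are baseline, four changed levels, and baseline again.
- Intervention / Protocol: "Measurements will be performed once daily for up to three consecutive days or until the patient is extubated".
- The same part gives the one reduction of repeated data: "All values will be averaged across the three readings". This collapses readings within a step, not steps or days.
- Sample Size: "we plan to enroll a total of 40 patients".

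The next bullet under Secondary analysis does deal with clustering, but for a different question: "Linear mixed models will explore associations between PS levels and effort parameters, accounting for intra-patient variability". The section closes with a general rule: "A p-value <0.05 will be considered statistically significant".

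**The concern.** The usual tests for Pearson and Spearman coefficients assume that each pair of values is independent of the others. Here up to 18 pairs come from the same patient, and both indices are likely to carry a patient-level component. If all pairs are used, the test counts far more information than there is.

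The second problem remains even if nobody reads the p-value. A pooled coefficient is a weighted blend of two relations: whether patients with a high value on one index tend to have a high value on another, and whether the indices move together in a given patient as support changes. Since the study is about responses to changed support, a reader will probably take the coefficient as evidence on the second, which it cannot isolate.

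**Working it through.** **The plan's own figure.** The protocol gives no figure for the correlation analysis. Its one computed figure, 20 patients for the paired t-test, reproduces closely: effect size 0.8, two-sided alpha 0.05 and power 0.90 give 18.45, so 19, and power at 20 is 92.4%. Nothing below bears on it.

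**Inputs from the protocol.** 40 patients; 6 step records per session; up to 3 sessions. So m = 6 × 1 = 6 to 6 × 3 = 18 records per patient, and at most 40 × 18 = 720 records.

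**Assumed inputs.** The documents give no ICC, so a range of 0.1 to 0.7 is used, the same for both indices. Every patient is taken to supply all m records. For the error rates, the two indices are truly unrelated.

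**False-positive rate.** With clusters of size m, the variance of r is inflated by

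V = 1 + (m − 1) × ICC²,

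and the test at nominal 5% rejects with probability 2 × [1 − Φ(1.96 / √V)].

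| ICC | V, one day (m = 6) | Rejects | V, three days (m = 18) | Rejects |
|---|---|---|---|---|
| 0.1 | 1.05 | 5.6% | 1.17 | 7.0% |
| 0.3 | 1.45 | 10.4% | 2.53 | 21.8% |
| 0.5 | 2.25 | 19.1% | 5.25 | 39.2% |
| 0.7 | 3.45 | 29.1% | 9.33 | 52.1% |

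Simulation with 40 patients agrees within simulation error. For Pearson over three days, 2,000 runs per setting gave 7.5%, 23.1%, 39.5% and 52.5%. Spearman over three days gave 20.0%, 35.4% and 51.1% at ICC 0.3, 0.5 and 0.7.

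At ICC 0.5 over three days, the nominal SD of r near zero is 1/√720 = 0.037. The actual SD is 0.037 × √5.25 = 0.085. The 720 records carry the information of 720 / 5.25 = 137 independent ones.

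**Blending.** With equal ICC for both indices, the pooled coefficient is approximately

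r(pooled) = ICC × r(between) + (1 − ICC) × r(within).

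At ICC 0.5:

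- within 0.8, between 0: 0.5 × 0 + 0.5 × 0.8 = 0.40 (simulated 0.41);
- within 0, between 0.8: 0.5 × 0.8 + 0.5 × 0 = 0.40 (simulated 0.39);
- between +0.6, within −0.6: 0.30 − 0.30 = 0 (simulated −0.02).

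**Does a remedy hold its level?** With a patient effect only, the correlation of patient means rejected 4.2–6.0% and the patient-centred correlation 4.5–5.5%. With day-to-day variation within patient as well, patient centring is not enough. At assumed variance shares of 0.3 patient, 0.2 day and 0.5 residual it rejected between 9% and 10%; at 0.2, 0.3 and 0.5, about 13%. Centring within patient and day held about 5% in both cases.

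**The case against.** The strongest reply is that pooling is inferred. The bullet names a coefficient and stops. Correlations at baseline only, at each support level, on patient means or on change scores would all fit it, and with one pair per patient the test holds about 5%. The authors plainly know the data are clustered: the primary analysis is repeated-measures ANOVA or Friedman, and the neighbouring bullet uses mixed models. A reader might infer that the protocol states that it treats all records as independent. It does not. But it names a method and, beside it, a design to which that method does not apply without a further step that it leaves out. The mixed models cover support level against effort, so they do not supply that step for index against index. One pair per patient would also say nothing about co-movement within a patient, unless the pair is a change score.

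Three further points stand:

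- A true correlation of zero is unlikely. The Background presents Pocc and PMI as both reflecting inspiratory effort. The false-positive rate therefore measures how far the test is miscalibrated; it does not predict a false finding. Overstated precision and the blended coefficient matter more in practice. The protocol promises no confidence intervals for this analysis, so the point about intervals applies only if they are reported.
- A reader might infer that error rates must lie far above 5%. That depends on an ICC the documents do not give; at 0.1 the excess is slight.
- The three-day figures need all 18 records from all 40 patients. Extubation ends measurement, and the Safety and Tolerability rules can cut a session short.

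**Conclusion.** The point holds on the plain reading of the protocol. An ordinary correlation is specified for data with up to 18 records per patient, no reduction to one pair per patient is stated, and the result would be overstated precision and a coefficient that cannot be interpreted as either a within- or a between-patient relation. The blending is the firmer part, since it does not depend on testing a null of zero.

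The inflation is conditional: roughly 5–7% at ICC 0.1, rising to 29–52% at ICC 0.7, for complete records on one to three days from 40 patients. These are upper-end values for each ICC. If the correlations are in fact run on one pair per patient, the objection to the p-values falls and what remains is a missing statement of the unit of analysis.

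A reader might also infer that the study's main conclusions are at risk. They are not. Index-to-index correlation is not among the listed primary or secondary outcomes, the study describes itself as exploratory, and neither the primary analysis nor the sample size depends on this line. It should be corrected, but it is no obstacle to the study.

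**What to change.** Replace the bullet with text that states the unit of analysis and separates the two relations:

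1. **Within patient:** a correlation between indices after centring each within patient and day. Alternatively, a linear mixed model of one index on another, with random effects for patient and for day within patient, and the predictor split into its mean and its within-session deviation.
2. **Between patients:** a separate correlation on patient means.
3. **Intervals:** from the mixed model or from a bootstrap that resamples whole patients.

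The day level should be included, because centring on patient alone left rejection at about 9–13% when day-to-day variation was assumed.

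The cost is one revised bullet and a few lines of R, the software already named; no new data are needed. The between-patient estimate will rest on 40 patients, with an SD near zero of about 1/√39 = 0.16, instead of up to 720 records. The within-session estimate need not lose much precision: with complete data it has 720 − 120 − 1 = 599 degrees of freedom, so an SD near zero of about 1/√599 = 0.041, against the nominal 0.037 of the pooled analysis. The main change there is in what is estimated.

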All data will be prospectively collected during each predefined pressure support (PS) level (baseline, ± 3 cmH₂O, ± 6 cmH₂O), following a 2-minute stabilization period at each step. The following variables will be recorded:

1. Demographics and Baseline Clinical Data

- Age, sex, height, weight, BMI
- Primary diagnosis and operation
- APACHE II or SOFA score at ICU admission
- Time from intubation to enrollment (hours)
- Baseline ventilator settings (PEEP, FiO₂, baseline PS)
- Baseline arterial blood gas (ABG): pH, PaCO₂, PaO₂, HCO₃⁻, SaO₂

2. Ventilatory and Physiological Parameters (at each PS level)

- Tidal volume (Vt) – measured from ventilator display
- Respiratory rate – measured from ventilator
- Minute ventilation (MV) – calculated
- P_{0.1} – occlusion pressure at 0.1 seconds
- P_{occ} – airway pressure drop during inspiratory hold
- PMI – pressure muscle index calculated as P_{plat} – (PEEP + PS)
- P_{plat} – plateau pressure (via inspiratory hold)
- P_{peak} – peak inspiratory pressure
- Crs – static compliance: Vt / (P_{plat} – PEEP)
- SpO₂ – peripheral oxygen saturation (pulse oximetry)
- EtCO₂ – end-tidal CO₂ if available
- HR and MAP – heart rate and mean arterial pressure (non-invasive or arterial line)
- Use of accessory muscles – observational note
- Signs of distress or dyssynchrony – e.g., paradoxical breathing, anxiety, diaphoresis

4. Post-Protocol Clinical Follow-up

- Duration of mechanical ventilation after study (in hours)
- Need for reintubation or non-invasive ventilation within 48 h
- Total ICU length of stay (LOS)
- ICU and hospital discharge status
- Complications: VAP, barotrauma, unexpected weaning failure

Safety and Tolerability

The protocol allows immediate cessation of PS level changes and return to baseline settings if any of the following occur:

- Respiratory rate >35 breaths/min
- SpO₂ < 90%
- HR > 140 bpm or >30% change from baseline
- Signs of distress: diaphoresis, agitation, anxiety
- Hemodynamic instability

Sample Size

This is an exploratory physiological study using a repeated-measures design. Based on prior literature (Docci et al., 2023; Umbrello et al., 2015), a within-subject difference in

the pressure muscle index (PMI) of approximately 2.0 cmH₂O (standard deviation ~2.5) between pressure support (PS) levels is considered clinically meaningful.

Using a two-sided paired t-test with the following assumptions:

- Alpha (α) = 0.05
- Power (1 - β) = 0.90
- Effect size = 0.8

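### The only method named for relating response pattern to outcome is logistic regression, with prolonged ventilation as its example; cutting ventilation hours into yes/no discards power that 40 patients can ill spare (minor)

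*Protocol*

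**What the plan says.** Under Measurements and Outcomes, one secondary outcome is "To assess the relationship between these ventilatory response patterns and clinical outcomes, including duration of mechanical ventilation, ICU length of stay", followed by reintubation or non-invasive ventilation and discharge disposition. The end of the Background gives the same question more weight, as part of the second of two primary objectives.

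Data Collection, item 4 (Post-Protocol Clinical Follow-up), records "Duration of mechanical ventilation after study (in hours", "Total ICU length of stay (LOS" with no unit given, "Need for reintubation or non-invasive ventilation within 48 h", discharge status and complications.

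Statistical Analysis, Secondary analysis, says that the incidence of under- and over-assistance will be described and that "logistic regression may be used to assess their associations with clinical outcomes (e.g., prolonged ventilation". No cut-off for prolonged ventilation is given. The other secondary methods serve other questions: correlation relates the effort indices to one another, and the linear mixed models relate pressure support level to effort.

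On size, the Sample Size section says "we plan to enroll a total of 40 patients". The patterns are to be assigned post hoc, so the group split is unknown in advance.

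**The concern.** Two of the listed outcomes are durations, and one of these is explicitly recorded in hours. Logistic regression can use a duration only after it has been cut into yes/no. The single example in the text, prolonged ventilation, is such a cut. The cut treats two patients on the same side of the threshold as identical, however far apart their hours are. With 40 patients in two groups of unknown size, that loss matters: a real and fairly large association could be reported as absent.

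For the outcomes that are binary by nature, a different difficulty may arise. If events are few, one pattern group may have none, and maximum-likelihood logistic regression then gives no finite odds ratio to report.

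**Working it through.** **The plan's own figure.** The protocol's calculation is for the within-patient PMI comparison, not for this question. It is introduced by "Using a two-sided paired t-test with the following assumptions": "Alpha (α) = 0.05", power 0.90, effect size 2.0/2.5 = 0.8. The normal approximation is ((1.960 + 1.282)/0.8)² = 16.4, so 17 patients. The noncentral t gives 19 (power 0.909), and at 20 patients power is 0.924. The stated minimum of 20 is sound. No power is stated for the pattern-outcome comparison.

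**Inputs for the check.** From the protocol: N = 40, α = 0.05, taken as two-sided. Assumed, because the protocol does not give them: a split of 20/20 or 10/30, log-normal durations all observed, group shifts of 0.5 or 1.0 SD on the log scale, and event rates of 5–20%.

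**Durations, exact cross-check at a 1 SD shift.** For the uncut comparison, the noncentrality is 1/√(1/n₁ + 1/n₂).
- 20/20: 1/√(1/20 + 1/20) = 3.16, giving 86.9% power (t-test). A cut at the pooled median lies 0.5 SD from each group mean, so the proportions above it are 69% and 31%. Enumerating all 2×2 tables gives logistic power of 67% (likelihood-ratio) or 66% (Wald).
- 10/30: 1/√(1/10 + 1/30) = 2.74, giving 76.1%. The median cut gives 58% (likelihood-ratio) or 41% (Wald).

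**Durations, simulation with the cut taken from the sample** (at least 4,000 data sets per setting; ranges span the Wald and likelihood-ratio tests and repeated runs):

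| Split | Shift | Rank test, uncut | Logistic, median cut | Logistic, 70th-percentile cut |
|---|---|---|---|---|
| 20/20 | 1.0 SD | about 85% | about 61% | 70–75% |
| 10/30 | 1.0 SD | about 72% | 55–62% | 58–59% |
| 20/20 | 0.5 SD | about 31% | 16–17% | about 30% |

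At 20/20 and 1 SD, the median cut costs 85 − 61 = 24 points, or 24/85 = 28% of the available power. At 0.5 SD a cut at the 70th percentile loses almost nothing, but power is then poor with any method.

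**Time-to-event alternative, for context.** With 40 events and a 20/20 split, power is Φ(√(40/4)·ln HR − 1.96). At a hazard ratio of 2 this is Φ(3.162 × 0.693 − 1.96) = Φ(0.23) = 59%. At 1.5 and 2.5 it is 25% and 83%.

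**Binary outcomes, no true association.** The chance that at least one group has no events is 1 − [1 − (1−p)^n₁][1 − (1−p)^n₂]. For p = 0.10 and 20/20, 0.9²⁰ = 0.1216, so 1 − 0.8784² = 0.228. In full:

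| Event rate | 20/20 | 10/30 |
|---|---|---|
| 5% | 59% | 69% |
| 10% | 23% | 38% |
| 20% | 2% | 11% |

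At a 10% rate and 20/20, the true size of a nominal 5% test is 0.2% for Wald and 8.5% for likelihood-ratio; the Firth penalised-likelihood test has 3.9%. Over event rates of 5–20% and both splits, Firth's size is 1.2–4.9%, with the lowest values at a 5% rate.

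**Power for binary outcomes at 20/20.**
- 40% v 10%: Wald 46%, likelihood-ratio 62.5%, Firth 61%, Fisher 49%.
- 50% v 5%: Wald 57%, likelihood-ratio 94.5%, Firth 94%.

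**The case against.** The text is permissive. It says that logistic regression may be used, in a study that calls itself exploratory, and gives prolonged ventilation only as an example. Nothing forbids analysing the hours as recorded, and a statistical analysis plan that is not shown may do so. A reader might infer that the protocol requires every duration to be cut, ICU stay included. It does not: only ventilation duration appears in yes/no form. Nor is the silence on other methods a fault in itself. What stands is narrower: the one method and the one example that the protocol does offer for a stated objective are a poor use of data already collected.

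A reader might also infer that logistic regression wastes much of the power for binary events and that a penalised method restores it. The documents do not support this. They name no Wald test, and a likelihood-ratio test of the same model matches Firth at 20/20 in the two contrasts shown. At 10/30, with the higher risk in the larger group (40% v 10%), likelihood-ratio power is 52% against Firth's 41%. Fisher's test is not a reliable gain either: for 40% v 10% at 10/30, with the higher risk in the smaller group, it has 47% power against Wald's 52%. The case for penalisation is finite estimates and control of size, not power.

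Sparseness is itself an assumption. With a 20/20 split and a 20% event rate, an empty group occurs about 2% of the time. Finally, the analysis sentence speaks of under- and over-assistance while the outcomes speak of active and quasi-passive patterns, and the protocol does not map one to the other. The argument about cutting a duration is the same for either grouping.

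**Conclusion.** The point holds as a minor, inexpensive improvement. Dichotomising ventilation hours loses power under both logistic tests: about 85% falls to 61–75% at 20/20, and about 72% to 55–62% at 10/30, for a 1 SD shift in log-normal durations among 40 patients. The loss depends on the cut-off and the split, and all durations were assumed observed; death was not modelled. Analysing the hours uncut does not make the study adequate for moderate associations.

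The binary-outcome part is conditional. At event rates of 5–10%, an empty group has a 23–59% chance (20/20) or 38–69% (10/30). At a 10% rate with a 20/20 split, neither ordinary test holds 5%. At rates of 20% or more with balanced groups, the problem largely disappears. The PMI, Pocc and P0.1 analyses and the sample size are unaffected.

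**What to change.** In Statistical Analysis, Secondary analysis, replace the logistic regression sentence with two statements:

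1. Duration of mechanical ventilation and ICU length of stay will be compared between patterns on their recorded scale by a rank-based or time-to-event method, not as a yes/no prolonged-ventilation outcome. State how death is handled, for example as a competing event or as the worst rank; discharge status is already collected.
2. Logistic regression will be used for the truly binary outcomes, with Firth-penalised estimates and penalised-likelihood p-values and intervals when events are sparse.

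The cost is one or two sentences and no new data. The downsides are that duration results will not be odds ratios, that death needs an explicit rule, and that penalised odds ratios are shrunk slightly towards 1 with a conservative test at very low event rates (size 1.2–2.3% at a 5% rate).
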